4.3.1 Dose delays: nivolumab

There will be no dose modifications allowed for management of toxicities. Should the treating physician decide to delay treatment given suspicion for a drug-related side effect, the side effect should be attributed to one study drug to the best of the physician's ability. Nivolumab should be delayed based on this attribution, or both drugs if a definite attribution is not possible. Nivolumab can be held for a maximum of 56 days.

Nivolumab administration should be delayed for the following until resolution to \leq Grade 1 or baseline:

- Any Grade \geq 2 non-skin, drug-related adverse event, with the following exceptions:
 - Grade 2 drug-related fatigue or laboratory abnormalities do not require a treatment delay

NU Study Number: NU 16L04
Other Study Number: CA 209-801

- Any Grade 3 skin, drug-related adverse event
- Any Grade 3 drug-related laboratory abnormality, with the following exceptions for lymphopenia, leukopenia, AST, ALT, or total bilirubin:
 - Grade 3 lymphopenia or leukopenia does not require dose delay
 - If a subject has a baseline AST, ALT or total bilirubin that is within normal limits, delay dosing for drug-related Grade ≥ 2 toxicity
 - If a subject has baseline AST, ALT, or total bilirubin within the Grade 1 toxicity range, delay dosing for drug-related Grade ≥ 3 toxicity

Any adverse event, laboratory abnormality, or intercurrent illness which, in the judgment of the investigator, warrants delaying the dose of study medication.

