4.3.2 Treatment discontinuation: nivolumab

Should the treating physician decide to discontinue treatment given suspicion for a drug-related side effect, the side effect should be attributed to one study drug to the best of the physician's ability. Nivolumab should be discontinued based on this attribution, and the patient must come off study treatment. The patient may not receive metformin monotherapy on-study.

Nivolumab should be discontinued permanently for the following:

- Any Grade 2 drug-related uveitis, eye pain, or blurred vision that does not respond to topical therapy and does not improve to Grade 1 severity within the re-treatment period OR requires systemic treatment
- Any Grade 3 non-skin, drug-related adverse event lasting > 7 days, with the following exceptions for laboratory abnormalities, drug-related uveitis, pneumonitis, bronchospasm, hypersensitivity reactions, infusion reactions, and endocrinopathies:
 - Grade 3 drug-related uveitis, pneumonitis, bronchospasm, hypersensitivity reaction, or infusion reaction of any duration requires discontinuation
 - Grade 3 drug endocrinopathies adequately controlled with only physiologic hormone replacement do not require discontinuation
 - Grade 3 drug-related laboratory abnormalities do not require treatment discontinuation except:
 - Grade 3 drug-related thrombocytopenia > 7 days or associated with bleeding (aside from minor bleeds \leq Grade 1) requires discontinuation
 - Any drug-related liver function test (LFT) abnormality that meets the following criteria require discontinuation:
 - AST or ALT $> 5-10 \times$ ULN for > 2 weeks
 - AST or ALT $> 10 \times$ ULN
 - Total bilirubin $> 5 \times$ ULN
 - Concurrent AST or ALT $> 3 \times$ ULN and total bilirubin $> 2 \times$ ULN
- Any Grade 4 drug-related adverse event or laboratory abnormality, except for the following events which do not require discontinuation:
 - Grade 4 neutropenia < 7 days
 - Grade 4 lymphopenia or leukopenia
 - Isolated Grade 4 amylase or lipase abnormalities that are not associated with symptoms or clinical manifestations of pancreatitis. PI and Data and Safety Monitoring Committee (DSMC) should be consulted for Grade 4 amylase or lipase abnormalities.

NU Study Number: NU 16L04
Other Study Number: CA 209-801

- Isolated Grade 4 electrolyte imbalances/abnormalities that are not associated with clinical sequelae and are corrected with supplementation/appropriate management within 72 hours of their onset

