- Grade 4 drug-related endocrinopathy adverse events, such as adrenal insufficiency, ACTH deficiency, hyper- or hypothyroidism, or glucose intolerance, which resolve or are adequately controlled with physiologic hormone replacement (corticosteroids, thyroid hormones) or glucose-controlling agents, respectively, may not require discontinuation.
- Any event that leads to interruption in dosing lasting > 4 weeks from the previous dose requires discontinuation, with the following exceptions:
 - Dosing interruptions to allow for prolonged steroid tapers to manage drug-related adverse events are allowed. Prior to re-initiating treatment in a subject with a dosing interruptions lasting > 4 weeks from the previous dose, the PI and DSMC must be consulted. Tumor assessments should continue as per protocol even if dosing is interrupted. Periodic study visits to assess safety and laboratory studies should also continue every 4 weeks or more frequently if clinically indicated during such dosing interruptions.
 - Dosing interruptions lasting > 4 weeks from the previous dose that occur for non-drug- related reasons may be allowed if approved by the PI and DSMC. Prior to re-initiating treatment in a subject with a dosing interruption lasting > 4 weeks, the PI and DSMC must be consulted. Tumor assessments should continue as per protocol even if dosing is interrupted. Periodic study visits to assess safety and laboratory studies should also continue every 4 weeks or more frequently if clinically indicated during such dosing interrupted.
 - Any adverse event, laboratory abnormality, or intercurrent illness, which in the judgment of the Investigator, presents a substantial clinical risk to the subject with continued nivolumab dosing.
 - If the patient is still receiving clinical benefit, he or she can hold drug for a maximum of 8 weeks (56 days) and subsequently continue therapy following the original treatment schedule.

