NU Study Number: NU 16L04
Other Study Number: CA 209-801

Table 4-2: Nivolumab Infusion Reactions		
NCI CTCAE Grade	Treatment	Premedication at subsequent dosing
	
subject until recovery of the symptoms
 
In case of late-occurring hypersensitivity symptoms (eg, appearance of a localized or generalized pruritus within 1 week after treatment), symptomatic treatment may be given (eg, oral antihistamine or corticosteroids)
	

Immunotherapy agents such as nivolumab are associated with AEs that can differ in severity and duration compared to other therapeutic classes of medications. Early recognition and management of AEs associated with nivolumab can mitigate severe toxicity. Corticosteroids are the primary therapy for drug-related AEs. Management algorithms have been developed to assist investigators in assessing and managing nivolumab associated AEs, which can be found in Appendix D of this protocol. The guidance provided in these algorithms should not replace the Investigator's medical judgment.

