Patients on IV steroids may be switched to an equivalent dose of oral corticosteroids (e.g. prednisone) at start of tapering or earlier, once sustained clinical improvement is observed. Lower bioavailability of oral corticosteroids should be taken into account when switching to the equivalent dose of oral corticosteroids.

Pulmonary Adverse Event Management Algorithm

[figure not shown]
Rule out non-inflammatory causes. If non-inflammatory cause, treat accordingly and continue I-O therapy. Evaluate with imaging and pulmonary consultation.

Patients on IV steroids may be switched to an equivalent dose of oral corticosteroids (e.g. prednisone) at start of tapering or earlier, once sustained clinical improvement is observed. Lower bioavailability of oral corticosteroids should be taken into account when switching to the equivalent dose of oral corticosteroids.

Renal Adverse Event Management Algorithm

[figure not shown]
Rule out non-inflammatory causes. If non-inflammatory cause, treat accordingly and continue I-O therapy

Patients on IV steroids may be switched to an equivalent dose of oral corticosteroids (e.g. prednisone) at start of tapering or earlier, once sustained clinical improvement is observed. Lower bioavailability of oral corticosteroids should be taken into account when switching to the equivalent dose of oral corticosteroids.

Skin Adverse Event Management Algorithm

Rule out non-inflammatory causes. If non-inflammatory cause, treat accordingly and continue I-O therapy.

Patients on IV steroids may be switched to an equivalent dose of oral corticosteroids (e.g. prednisone) at start of tapering or earlier, once sustained clinical improvement is observed. Lower bioavailability of oral corticosteroids should be taken into account when switching to the equivalent dose of oral corticosteroids.

*Refer to NCI CTCAE v4 for term-specific grading criteria.

**If SJS/TEN is suspected, withhold I-O therapy and refer patient for specialized care for assessment and treatment. If SJS or TEN is diagnosed, permanently discontinue I-O therapy.

NU Study Number: NU 16L04
Other Study Number: CA 209-801

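### For a diagnosed drug-related SJS or TEN event graded 3, Section 4.3 allows nivolumab to resume while the Appendix D skin footnote requires a permanent stop, and no text says which governs

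*Combined protocol and SAP*

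**What the plan says.** **Section 4.3.1 (dose delays).** The list opens with "Nivolumab administration should be delayed for the following until resolution to" Grade 1 or lower, or baseline. One item is "Any Grade 3 skin, drug-related adverse event", with no separate treatment of SJS or TEN. The section allows a hold of at most 56 days and ends with a line that lets the investigator delay for any event judged to warrant it.

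**Section 4.3.2 (permanent discontinuation).** The Grade 3 rule reads "Any Grade 3 non-skin, drug-related adverse event lasting > 7 days", so skin events fall outside it. The Grade 4 rule, "Any Grade 4 drug-related adverse event or laboratory abnormality", has no skin exclusion among its listed exceptions. Two further routes are general. One is "Any event that leads to interruption in dosing lasting > 4 weeks from the previous dose requires discontinuation", with exceptions. The other covers an event that, in the investigator's view, "presents a substantial clinical risk to the subject with continued nivolumab dosing". SJS and TEN are not mentioned.

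**Appendix D, skin algorithm footnote.** Immuno-oncology therapy is to be withheld if SJS/TEN is suspected. The footnote continues: "If SJS or TEN is diagnosed, permanently discontinue I-O therapy".

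**Status of Appendix D.** Its heading calls the algorithms recommended. Section 4.3.3, which refers the reader to them, says: "The guidance provided in these algorithms should not replace the Investigator's medical judgment".

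**The concern.** A site that works from the delay and discontinuation lists in Section 4.3 could re-treat a patient whose diagnosed Grade 3 SJS or TEN event has resolved, and would breach nothing in those lists. A site that works from Appendix D would stop nivolumab for good. Section 11.6 requires conduct exactly as the approved protocol describes, emergencies excepted, so sites need a single rule.

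Two things are at stake. The first is re-exposure after a serious skin reaction. The second is whether the patient stays on study treatment at all, because Section 4.3.2 takes a patient who discontinues nivolumab off study treatment and does not allow metformin alone.

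The mismatch looks like an incomplete update. The summary of changes shows that Amendment 3 added the footnote while aligning Appendix D with a newer Investigator Brochure. The same amendment edited Section 4.3.2, but only to rename the monitoring committee. The current text of Sections 4.3.1 and 4.3.2 has no matching SJS/TEN line.

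**Working it through.** This is a question of consistency between rules, so there is no figure in the plan to reproduce. The inputs are Sections 4.3.1, 4.3.2 and 4.3.3 and the Appendix D skin footnote, all in current text.

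| Situation | Section 4.3 | Appendix D footnote | Consistent? |
|---|---|---|---|
| SJS/TEN suspected, Grade 3 | Delay (4.3.1 skin item) | Withhold | Yes |
| SJS/TEN suspected, below Grade 3 | Delay open to the investigator (closing line of 4.3.1) | Withhold, if the footnote reaches this grade | Can be held under both |
| SJS/TEN diagnosed, Grade 4 | Discontinue (4.3.2 Grade 4 rule) | Discontinue | Yes |
| SJS/TEN diagnosed, Grade 3, resolves within the permitted hold | Delay, then may resume; no mandatory stop | Discontinue | **No** |

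Only the last row conflicts. The next step is to see whether another rule in Section 4.3 closes it.

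1. **Investigator-judgment item (4.3.2).** It has no skin exclusion and could lead to a stop. It depends on the investigator's view of risk, whereas the footnote depends on the diagnosis alone.
2. **Interruption rule (4.3.2).** It applies beyond 4 weeks, or 4 × 7 = 28 days, from the previous dose.
   - In Cycles 1–4 doses are 14 days apart, so a dose can slip by up to 28 − 14 = 14 days without triggering the rule.
   - From Cycle 5 the planned interval is itself 28 days, so a dose given later than day 28 exceeds it. An event that resolves before the next dose is due causes no interruption.
   - Where the rule is triggered, prolonged steroid tapers are exempt, subject to consultation with the PI and the DSMC before restart. A patient still benefiting may hold for up to 56 days and then continue.
   - The rule therefore catches some Grade 3 cases, depending on timing, and leaves others.
3. **Hypersensitivity line (4.3.2).** Grade 3 hypersensitivity requires discontinuation whatever its duration. That line sits under the bullet limited to non-skin events, so its application to SJS or TEN is at best unclear.
4. **Sections 4.6 and 4.8.** These allow removal for unacceptable toxicity or at the investigator's discretion. They say nothing specific to the diagnosis.

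None of these routes reproduces the footnote's unconditional instruction. For a resolved Grade 3 case, resuming nivolumab can comply with Section 4.3 and still contradict Appendix D.

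**The case against.** The strongest reply is that the two texts can both be obeyed. Section 4.3.1 sets a condition for delay and does not order re-treatment. An investigator can hold on suspicion and stop on diagnosis, using the judgment item in 4.3.2, without breaching any line. On this view the appendix, which is part of the protocol, adds a diagnosis-specific instruction to a general grade rule. This stands in part: no one is forced to re-treat, so the instructions are not strictly opposite. It does not remove the gap. The body permits what the footnote forbids, the algorithms are described as guidance that does not replace judgment, and no order of precedence is given.

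A second reply is that a Grade 3 SJS or TEN event is hypothetical. The protocol adopts CTCAE v4.03 without reproducing its grades for these events. If every case were Grade 4, both texts would stop nivolumab and there would be no conflict. This stands as a stated assumption. The summary of changes lists the footnote under the Grade 3–4 part of the skin algorithm, which suggests that it was meant to cover Grade 3.

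Some stronger readings are tempting but not supported:

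- **That Section 4.3 tells sites to keep dosing when SJS/TEN is suspected at Grade 1–2.** It does not. The closing line of 4.3.1 allows a delay. The footnote states no grade, the algorithm figure is not visible, and the Grade 3–4 label in the summary of changes points away from lower grades.
- **That a Grade 3 skin event can never lead to permanent discontinuation under Section 4.3.** The judgment item and the interruption rule can both lead there.
- **That the exclusion of patients with a history of SJS or TEN in Section 3.2.4 settles the on-study rule.** It is an entry criterion and does not govern dosing after enrolment.

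**Conclusion.** The inconsistency is real but confined to one situation: a diagnosed, drug-related SJS or TEN event, graded 3, that resolves within the permitted hold. There Section 4.3 allows nivolumab to resume, the Appendix D footnote requires a permanent stop, and precedence is unstated.

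The conclusion rests on two assumptions. The first is that such an event can carry Grade 3 under CTCAE v4.03. The second is that neither the judgment item nor the interruption rule has already ended treatment. The documents give no incidence, so the number of patients affected cannot be estimated.

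The consequence is for patient safety and for whether the individual patient remains on study treatment. The Simon two-stage sizes, error rates and response cut-offs are unaffected. The correction deserves to be made because the reaction is serious and the change is small. This review takes no position on which clinical rule is right.

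**What to change.** Reconcile Sections 4.3.1 and 4.3.2 with the Appendix D skin footnote, so that one explicit SJS/TEN entry covering suspected and diagnosed cases appears in the Section 4.3 lists and the two places agree. Add a sentence in Section 4.3 stating which text governs where it and Appendix D differ. While doing so, make clear which grades the footnote covers. The sponsor decides the clinical content of the entry.

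The cost is one or two lines in an amendment, with no extra test, visit or patient and no change to the statistical section.

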4.3.2 Treatment discontinuation: nivolumab

Should the treating physician decide to discontinue treatment given suspicion for a drug-related side effect, the side effect should be attributed to one study drug to the best of the physician's ability. Nivolumab should be discontinued based on this attribution, and the patient must come off study treatment. The patient may not receive metformin monotherapy on-study.

Nivolumab should be discontinued permanently for the following:

- Any Grade 2 drug-related uveitis, eye pain, or blurred vision that does not respond to topical therapy and does not improve to Grade 1 severity within the re-treatment period OR requires systemic treatment
- Any Grade 3 non-skin, drug-related adverse event lasting > 7 days, with the following exceptions for laboratory abnormalities, drug-related uveitis, pneumonitis, bronchospasm, hypersensitivity reactions, infusion reactions, and endocrinopathies:
 - Grade 3 drug-related uveitis, pneumonitis, bronchospasm, hypersensitivity reaction, or infusion reaction of any duration requires discontinuation
 - Grade 3 drug endocrinopathies adequately controlled with only physiologic hormone replacement do not require discontinuation
 - Grade 3 drug-related laboratory abnormalities do not require treatment discontinuation except:
 - Grade 3 drug-related thrombocytopenia > 7 days or associated with bleeding (aside from minor bleeds \leq Grade 1) requires discontinuation
 - Any drug-related liver function test (LFT) abnormality that meets the following criteria require discontinuation:
 - AST or ALT $> 5-10 \times$ ULN for > 2 weeks
 - AST or ALT $> 10 \times$ ULN
 - Total bilirubin $> 5 \times$ ULN
 - Concurrent AST or ALT $> 3 \times$ ULN and total bilirubin $> 2 \times$ ULN
- Any Grade 4 drug-related adverse event or laboratory abnormality, except for the following events which do not require discontinuation:
 - Grade 4 neutropenia < 7 days
 - Grade 4 lymphopenia or leukopenia
 - Isolated Grade 4 amylase or lipase abnormalities that are not associated with symptoms or clinical manifestations of pancreatitis. PI and Data and Safety Monitoring Committee (DSMC) should be consulted for Grade 4 amylase or lipase abnormalities.

NU Study Number: NU 16L04
Other Study Number: CA 209-801

- Isolated Grade 4 electrolyte imbalances/abnormalities that are not associated with clinical sequelae and are corrected with supplementation/appropriate management within 72 hours of their onset
- Grade 4 drug-related endocrinopathy adverse events, such as adrenal insufficiency, ACTH deficiency, hyper- or hypothyroidism, or glucose intolerance, which resolve or are adequately controlled with physiologic hormone replacement (corticosteroids, thyroid hormones) or glucose-controlling agents, respectively, may not require discontinuation.
- Any event that leads to interruption in dosing lasting > 4 weeks from the previous dose requires discontinuation, with the following exceptions:
 - Dosing interruptions to allow for prolonged steroid tapers to manage drug-related adverse events are allowed. Prior to re-initiating treatment in a subject with a dosing interruptions lasting > 4 weeks from the previous dose, the PI and DSMC must be consulted. Tumor assessments should continue as per protocol even if dosing is interrupted. Periodic study visits to assess safety and laboratory studies should also continue every 4 weeks or more frequently if clinically indicated during such dosing interruptions.
 - Dosing interruptions lasting > 4 weeks from the previous dose that occur for non-drug- related reasons may be allowed if approved by the PI and DSMC. Prior to re-initiating treatment in a subject with a dosing interruption lasting > 4 weeks, the PI and DSMC must be consulted. Tumor assessments should continue as per protocol even if dosing is interrupted. Periodic study visits to assess safety and laboratory studies should also continue every 4 weeks or more frequently if clinically indicated during such dosing interrupted.
 - Any adverse event, laboratory abnormality, or intercurrent illness, which in the judgment of the Investigator, presents a substantial clinical risk to the subject with continued nivolumab dosing.
 - If the patient is still receiving clinical benefit, he or she can hold drug for a maximum of 8 weeks (56 days) and subsequently continue therapy following the original treatment schedule.

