4.2 Treatment Administration

4.2.1 Nivolumab

Treatment will be administered on an outpatient basis. Reported adverse events and potential risks are described below. No investigational or commercial agents or therapies other than those described below may be administered with the intent to treat the patient's malignancy.

During Cycle 1-4, nivolumab will be administered at a fixed dose of 240 mg intravenously over approximately 30 minutes (-5 / +15 minutes) every 14 days. Starting with Cycle 5, nivolumab will be administered at 480mg IV over 60 minutes (-10 / +15 minutes) every 28 days until disease progression, intolerable toxicity, or withdrawal of consent.

There will be no dose escalations or reductions of nivolumab allowed. Subjects may be dosed no less than 12 days or 24 days from the previous dose (for 240 mg and 480 mg doses, respectively). There are no pre-medications recommended for nivolumab on the first cycle. If an acute infusion reaction is noted, subjects should be managed according to Section 4.3.3.

Nivolumab is to be administered as a 30-minute (-5 / +15 minutes) or 60-minute (-10 / +15± minutes) IV infusion (for 240mg and 480mg respectively), using a volumetric pump with a 0.2- 1.2 micron low-protein binding in-line filter at the

NU Study Number: NU 16L04
Other Study Number: CA 209-801

protocol-specified dose. The drug can be infused undiluted or diluted so as not to exceed a total infusion volume of 120mL. It is not to be administered as an IV push or bolus injection. At the end of the infusion, flush the line with a sufficient quantity of normal saline.

Subjects will be monitored continuously for AEs while on study. Treatment delay or discontinuation will be based on specific laboratory and adverse event criteria.

Early recognition and management may mitigate severe toxicity. Evaluation and Management Guidelines were developed to assist investigators and can be found in the Investigator Brochure:

- Suspected Pulmonary Toxicity
- Diarrhea and Colitis
- Suspected Hepatotoxicity (including asymptomatic liver function tests [LFT] elevations)
- Suspected Endocrinopathy
- Nephrotoxicity

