8. The same modality used at baseline should be used throughout for imaging. CT imaging with contrast will occur every 2 cycles starting with Cycle 3 Day 1 (\pm 7 days) and should include chest, abdomen, and pelvis. Neck will be included only if measurable lesions are present. Metformin should be held prior to scans per each institutional protocol. Tumor measurements will be performed using RECIST 1.1. Progressive Disease (PD) must be confirmed by repeat scan within 8 weeks at least after 4 weeks. Patients with a known history of CNS disease must have CNS imaging at screening to rule out activity.
9. Patients will undergo a fresh tissue biopsy prior to study enrollment, unless deemed to be clinically inappropriate per PI. If not feasible, archived tissue will be used (if available).
10. The maximum time interval between registration and the first dose of study drug will be 14 days
11. Nivolumab will be given as follows:
Cycle 1-4: 240mg IV over 30 minutes (-5 / +15 minutes) every 14 days (Day 1 & 15, \pm 3 days)
Cycle 5+: 480mg IV over 60 minutes (-10 / +15 minutes) every 28 days (Day 1, \pm 3 days) until disease progression, intolerance, or withdrawal of consent.
12. Metformin will be dispensed Day 1 of each cycle. Dosing will begin at 1,000mg po once daily and escalate by 500mg every 7 days until the final dose of 2,000mg is reached. Patients will return unused drug and drug bottles at each study visit and will maintain a drug diary to track compliance.
13. The end of treatment visit should occur 30 days after the last dose of study treatment (+/- 7 days) or before starting another line of treatment, whichever comes first.
14. Correlatives from peripheral blood will be collected for all patients at Induction Day 1, C1D1, C3D1, and at the EOT. Biopsy samples (fresh or archived) will be collected for all patients if possible. See separate lab manual for specifications. See section 9.0 for details.
15. Metformin monotherapy will be given at 1,000mg PO QD during the 7-day Induction period, prior to starting nivolumab on Cycle 1 Day 1.
16. After patients come off treatment they will be followed up at 3, 6, 9, and 12 months (\pm 7 days) and then every 6 months (\pm 14 days) for 3 years for survival and progression of disease via either clinic visits or phone calls.

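### Before exceptions, the 4-week interruption limit in section 4.3.2 leaves no slack on 28-day nivolumab dosing, and its 56-day hold does not match the one in section 4.3.1

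*Combined protocol and SAP*

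**What the plan says.** Nivolumab is given every 14 days in Cycles 1–4 and every 28 days from Cycle 5 (sections 4.1 and 4.2.1). Footnote 11 of the study procedures table (section 5.0) gives the later schedule as "480mg IV over 60 minutes (-10 / +15 minutes) every 28 days", with a window of ±3 days on Day 1.

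The minimum gap is stated separately for each dose in section 4.2.1: "Subjects may be dosed no less than 12 days or 24 days from the previous dose (for 240 mg and 480 mg doses, respectively".

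The maximum gap is not. Section 4.3.2 has one rule for both schedules: "Any event that leads to interruption in dosing lasting > 4 weeks from the previous dose requires discontinuation, with the following exceptions". The exceptions listed are:

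- prolonged steroid tapers for drug-related events, with the principal investigator and the safety monitoring committee (DSMC) consulted before restarting;
- interruptions for reasons unrelated to the drug, if those two approve;
- as the list appears in the text, a hold conditional on benefit: "If the patient is still receiving clinical benefit, he or she can hold drug for a maximum of 8 weeks (56 days".

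Section 4.3.1, which governs dose delays, says without any condition: "Nivolumab can be held for a maximum of 56 days". Neither section says when the 56 days begin.

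**The concern.** A limit counted from the previous dose has to exceed the dosing interval to leave room for any delay. Here it equals the longer interval. A toxicity delay of a few days, unremarkable in Cycles 1–4, becomes a stopping event or a committee matter from Cycle 5, and the protocol gives no reason for the difference.

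The second problem is that 4.3.1 and 4.3.2 answer the same question differently. Section 4.3.1 requires a delay until the event returns to Grade 1 or baseline and permits up to 56 days. Section 4.3.2 can require the same patient to stop.

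The rule matters because stopping nivolumab for a drug-related effect ends all study treatment; 4.3.2 does not allow metformin alone on study. It may also reach the primary analysis. Section 4.7 counts a response seen after stopping for an adverse event, but section 6.3 makes patients removed from the study for adverse drug reactions non-evaluable. Two investigators reading the text in good faith could handle the same patient differently.

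**Working it through.** The plan states no figure for allowed delay, so there is none to reproduce. The check is day arithmetic followed by a comparison of the two sections.

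**Inputs.** Limit: 28 days from the previous dose (4.3.2). Intervals: 14 and 28 days (4.1, 4.2.1). Window: ±3 days (5.0, footnote 11). Maximum hold: 56 days (4.3.1, 4.3.2).

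**Step 1: when 28-day dosing begins.** With C1D1 as day 1, C5D1 = 1 + 4 × 28 = day 113. The first dose due after a 28-day interval is C6D1 = 113 + 28 = day 141.

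**Step 2: day counts on each schedule.**

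| Quantity (days) | 14-day dosing | 28-day dosing |
|---|---|---|
| Delay past due date before exceptions (limit − interval) | 28 − 14 = 14 | 28 − 28 = 0 |
| Longest in-window gap, previous dose on time | 14 + 3 = 17 | 28 + 3 = 31 |
| Longest in-window gap, previous dose 3 days early | 14 + 6 = 20 | 28 + 6 = 34 |
| Delay past due date under a 56-day hold counted from the previous dose (assumption) | 56 − 14 = 42 | 56 − 28 = 28 |
| Gap between doses if the 56 days run from the missed dose (assumption) | 14 + 56 = 70 | 28 + 56 = 84 |

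On 14-day dosing every in-window gap is inside the 28-day limit. On 28-day dosing the late edge of the window exceeds it by 3 or 6 days.

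**Step 3: the two sections side by side, more than 4 weeks after the previous dose.** This covers events not already stopped by the Grade 3–4 rules of 4.3.2.

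| Reason for delay | 4.3.1 | 4.3.2 |
|---|---|---|
| Drug-related, steroid taper | up to 56 days | allowed; consult before restart |
| Not drug-related | up to 56 days | may be allowed with approval |
| Drug-related, no taper, patient benefiting | up to 56 days | up to 56 days, if the last bullet is an exception |
| Drug-related, no taper, patient not judged to be benefiting | up to 56 days | discontinue |

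The last row is where the answers conflict outright. It is not empty. Section 4.3.1 requires a delay for "Any Grade 3 skin, drug-related adverse event" and for most Grade 2 non-skin events, while the duration-based stopping rule in 4.3.2 covers "Any Grade 3 non-skin, drug-related adverse event lasting > 7 days". A slow Grade 3 skin event or a slow Grade 2 non-skin event is therefore held under one section and not yet stopped by the grade rules of the other.

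**Step 4: position relative to the primary endpoint.** Section 10.1 measures response at 24 weeks from the start of treatment. Counted from C1D1 this is 1 + 168 = day 169, which is also nominal C7D1 (141 + 28). Only the C6D1 dose falls clearly before it.

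**The case against.** The strongest reply is that the exceptions do most of the work. Patients on 28-day dosing have been scanned at C3D1 and C5D1, and treatment normally stops at progression (4.6). A patient without progression at week 16 has at least 12 weeks of stable disease, which section 10.3 counts as clinical benefit, and section 4.4 lets patients with confirmed progression continue only if they still benefit. Long holds are also often steroid-treated: "Corticosteroids are the primary therapy for drug-related AEs". This largely stands and is why few patients would be affected. It does not remove the defect. Section 10.3 defines an analysis rate, section 4.4 illustrates benefit by symptoms and tolerance, and 4.3.2 defines nothing, so a patient on hold for toxicity could be classified either way.

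A reader might infer that any Cycle 5+ dose given on day 29, 30 or 31 forces discontinuation. The documents do not support that. The rule needs an event that interrupts dosing, and a dose inside the ±3-day window is best read as on schedule. The 31- and 34-day figures show that the limit and the window were not reconciled, not that compliant patients must stop.

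It can also be said that 56 days in 4.3.1 is a ceiling, with 4.3.2 the more specific stopping rule. A site could follow both that way, but the text does not say which section governs.

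Finally, the list structure in 4.3.2 is doubtful: the bullet just before the clinical-benefit one, on events posing substantial risk, is plainly a reason to stop, yet appears among the exceptions. If the clinical-benefit bullet is not an exception either, the conflict with 4.3.1 is broader, because the 4-week stop then has no carve-out for benefiting patients.

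**Conclusion.** The rule is wrong as written, and the matter is minor. Before exceptions it allows 14 days of delay on one schedule and 0 on the other, starting with the dose due on nominal day 141. After exceptions, the outright disagreement between 4.3.1 and 4.3.2 is confined to drug-related delays beyond the 4-week limit, without a steroid taper, in patients not judged to be benefiting. This assumes that the last bullet of 4.3.2 is an exception and that in-window doses are on schedule. The number of patients cannot be derived from the documents.

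It would be tempting to conclude that the two-stage design is compromised. It is not: sample sizes, decision boundaries and error rates do not depend on this rule, and 4.7 still counts later responses. What can be said is that the rule could affect who is in the primary analysis set, through the evaluability exclusion in 6.3. How far depends on whether stopping treatment for toxicity is taken as removal from the study, which section 4.8 treats as a separate matter.

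**What to change.** In 4.3.2, state the interruption limit separately for the 14-day and 28-day schedules, or count it from the missed due date. As an example, 14 days past due equals 14 + 14 = 28 days from the previous dose on 14-day dosing, as now, and 28 + 14 = 42 days on 28-day dosing, both below 56. The clinical team should set the value. Add that doses given within ±3 days of the due date are not interruptions.

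In 4.3.1 and 4.3.2, state one 56-day maximum with the same condition and the same starting point. If the clinical-benefit condition is kept, define it, and make clear which bullets are exceptions to the 4-week rule.

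The cost is a wording amendment, with no change to sample size, visits or analyses. The downside is that some patients on 28-day dosing may have a longer gap before mandatory stopping or DSMC consultation.
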